3 OBJECTIVES AND ENDPOINTS

OBJECTIVES	ENDPOINTS	JUSTIFICATION FOR ENDPOINTS
Primary		
To identify imaging biomarkers that are associated with the probability of any reduction in pre-treatment baseline exacerbation frequency in a severe asthma population on biologics	Any reduction in exacerbations when compared to baseline exacerbations	Reduction in exacerbations is the primary clinical endpoint used in phase III trials to get many of the biologics used in asthma approved. Finding imaging biomarkers that associate with and possibly predict which patients will not have a reduction in exacerbations would be critical information for clinicians considering biologic initiation.
Secondary		
To identify imaging biomarkers that are associated with the probability of any post-treatment improvement of FEV1 of 5% or more	5% or greater improvement in FEV1 when compared to baseline FEV1	FEV1 is an important measure of lung function for patients with asthma, and any imaging biomarkers that predict a failure to improve this measure would be clinically useful.
To identify imaging biomarkers that are associated with the probability of any post-treatment reduction in maintenance OCS use	Any reduction in maintenance OCS use when compared to baseline OCS use	OCS are associated with multiple comorbidities, especially in the asthma population. Multiple phase III studies are currently underway to study maintenance OCS reduction in asthma due to this clinical concern and is a common reason for initiating biologics. Any imaging biomarkers that predict a failure to wean OCS after biologic initiation would be clinically useful.
Exploratory		
To identify imaging biomarkers that are associated with the probability of any reduction in pre-treatment baseline hospitalizations for asthma	Any reduction in hospitalizations when compared to baseline hospitalizations	Hospitalizations represent the most severe form of exacerbation and being able to find imaging biomarkers that associate with no improvement in hospitalizations would be clinically significant.
To identify imaging biomarkers that are associated with the probability of any post-treatment improvement in ACT score	Any improvement in ACT score when compared to baseline ACT score	Failure to improve symptoms after biologic initiation is a clinically frustrating scenario and finding imaging biomarkers that can predict this would be important for biologic initiation.

OBJECTIVES	ENDPOINTS	JUSTIFICATION FOR ENDPOINTS
To identify imaging biomarkers that are associated with the probability of any subjective post-treatment reduction in symptoms described clinically	Any subjective improvement of symptoms when compared to baseline subjective symptoms	Given the retrospective nature of our study, there is a high likelihood some of the other endpoint data will be missing from clinical encounters for our cohort. Clinical impression of symptoms, however, is expected to be present in essentially every clinical encounter for asthma. In order to make use of this important information, we opted to include an endpoint designed to capture this subjective data since finding imaging biomarkers that predict no improvement with this subjective marker would be clinically important, since this is a common reason clinicians seek to start severe asthma patients on biologic therapies.

4 STUDY DESIGN

4.1 OVERALL DESIGN

Over an 18-month period we plan to conduct our study in 3 parts as identified in the study timeline table above.

University of Michigan Cohort Discovery, Database Construction, and Baseline Analysis

We plan to utilize existing data analytic tools at the University of Michigan to search the EMR for eligible patients to include in a retrospective cohort as identified by the inclusion criteria in section 5. We estimate that approximately 300 subjects will meet our initial criteria based on a preliminary search. We will then abstract all available clinical information from the EMR, de-identify it (with coded key stored in a separate, secured location), and enter the resulting coded data into a database. Up to 2 years prior to biologic initiation or CT scan (whichever is earlier) and all post-biologic therapy information will be included. Clinical information we will abstract will include demographic information, heights, weights, comorbid illnesses (coded as malignancy, coronary artery disease, diabetes, stroke/TIA, cirrhosis, and CKD), non-biologic asthma medication dosage and frequency of use (OCS, ICS, SABA, LAMA, LABA, montelukast, zileuton, and theophylline), asthma biologic agent (benralizumab, reslizumab, mepolizumab, omalizumab, and dupilumab) start and (if applicable) end dates as well as reason for end date (coded as ineffective, cost, intolerance/allergy, non-compliance, lost to follow-up, and other), FeNO, ACT scores, serum and sputum eosinophil counts, IgE, pulmonary function test parameters (% predicted), hospital/emergency room/urgent care/unscheduled office visits and phone call encounters for asthma or breathing-related complaints, and subjective clinician assessment of asthma control (independently graded by 2 different clinicians interpretation of EMR data). Each subject will also be assigned a phenotype by the Severe Asthma Research Program criteria¹⁵. If a majority of subjects are missing post-bronchodilator data and unable to be clustered by these criteria, we will instead assign adopted clusters from this paper as follows: Cluster 3-Normal FEV1 ($\geq 68\%$ of predicted), eosinophils (< 200 cells/ μL), FeNO (< 25 ppb), and IgE (< 200 UI/ml) and no evidence of atopy; Cluster 4-Reduced FEV1 ($\leq 68\%$ of predicted) with abnormal elevation of eosinophils, FeNO, or IgE and/or evidence of atopy; Cluster 5--Reduced FEV1 ($\leq 68\%$ of predicted) with normal eosinophils, FeNO, or IgE and no evidence of atopy. We do not expect to have any Cluster 1 or 2 patients in our study but will assign them accordingly if present. We will perform similar abstraction procedures for approximately 200 patients in the University of Calgary cohort, and label the data with a tag for this cohort for analytical purposes.

For the purposes of our analysis, we will define baseline measurements as the average of all data obtained in the year prior to biologic initiation or, if only one clinical encounter (defined as an office or emergency room visit) is available in this time period, then the average of the 2 clinical encounters immediately prior to biologic initiation will be used with the time frame noted in the database. In order to assess our primary and secondary outcomes we will use the average of all data from 4 to 18 months after biologic initiation or, if only one clinical encounter is available in this time period, the average of the 2 clinical encounters closest to, but not before 4 months after, biologic initiation. If a second biologic is introduced or the initial biologic choice is

changed, we will use all clinical data prior to the change, even if it is before 4 months of use, then follow the above steps to collect new outcome data on the new drug (see **Figure 4**).

[figure not shown]

Figure 4. Baseline and Response Clinical Data Plan.

Since our interest is primarily in finding the ~15% of patients who do not respond to biologics, we have chosen to include partial and complete responders together in our endpoints in order to isolate the non-responder population. Table 1 below will represent the dichotomization of responders and non-responders for each endpoint using the baseline and post-biologic data as detailed above. An exacerbation will be defined as any hospitalization, urgent care, emergency room, or unscheduled office visit for asthma or a breathing-related complaint or a temporary increase of OCS or ICS dosing for 3 or more days with the intent of the increase to treat acute symptoms. For clinician response, clinical encounter notes will be read and interpreted by 2 independent physicians and graded as detailed in the table. Upon completion of all data abstraction the patient will be de-identified as described in data handling below.

	Responder	Non-responder
Exacerbations	Any decrease from baseline	No change from baseline
Hospitalizations	Any decrease from baseline	No change from baseline
Maintenance oral corticosteroid (OCS) use	Any decrease from baseline	No change from baseline

Change in FEV1	$\geq 5\%$ improvement from baseline	<5% improvement from baseline
ACT score	≥ 1 -point improvement from baseline	No change from baseline
Clinician impression of response to therapy	Any improvement in symptoms from baseline	No change from baseline

Table 1. Outcome Response Grading.

Morphomics CT Analysis and Clustering

After identification of all appropriate patients in the University of Michigan cohort, we will then identify all relevant CT scans in subjects. We will select pre-biologic CT data of the chest and, if available, abdomen/pelvis (or if no pre-biologic scans exist for a subject we will utilize CT imaging closest to the biologic start date and make note that the CT scan was obtained after biologic initiation) for analysis. Height-normalized measures will be computed to control for height-related correlation (e.g., Skeletal Muscle Index = Skeletal Muscle Area / Height²). Morphomics analysis will be run with measures centered and scaled into standard deviation units, stratified by sex and age. In addition, the Reference Analytic Morphomics Population¹⁶ will be used to generate additional variables that offer a population-based control for sex and age.

Analysis of Phenotypes, Training Data Set, and Assessing Model Robustness

Please see the statistical section for detailed statistical analysis plan.

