Study Population:	Approximately 300 male or female subjects ages 18-85 with a diagnosis of asthma and on biologic therapy will be studied at the University of Michigan in Ann Arbor, MI, USA and approximately 200 male or female subjects over the age of 18 will be studied in the University of Calgary in Calgary, Alberta, CA.
Description of Sites/Facilities	University of Michigan in Ann Arbor, MI, USA is a tertiary academic medical center. Rockyview General Hospital, associated with the
Enrolling Participants:	University of Calgary, Calgary, Alberta, Canada, is tertiary academic medical referral center for patients with severe asthma.
Study Duration:	1.5 years

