5.2 EXCLUSION CRITERIA

We will exclude patients with a > 10 pack year history of smoking and those with evidence of emphysema on CT imaging due to concerns that concurrent COPD may be attenuating the effects of the biologic. Those with some scattered bronchiectasis thought to be secondary to severe asthma will not be excluded; however, severe bronchiectasis secondary to other causes will be excluded for the same reason. Furthermore, patients who do not have accessible adequate follow-up information (4 or more months from drug initiation with clear documentation of response) will be excluded from the final analysis in part 3 due to an inability to assess response but will be included in the initial analysis to help with cluster identification.

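### The final analysis requires documented follow-up but no minimum observed period before the biologic, so an incompletely seen baseline year can class true improvers as having no reduction

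*Combined protocol and SAP*

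**What the plan says.** Section 4.1 defines the two windows whose comparison produces the primary label. For the first, "we will define baseline measurements as the average of all data obtained in the year prior to biologic initiation". For the second, "we will use the average of all data from 4 to 18 months after biologic initiation". If the baseline year holds only one encounter, "then the average of the 2 clinical encounters immediately prior to biologic initiation will be used with the time frame noted in the database".

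The look-back for abstraction has an upper limit only: "Up to 2 years prior to biologic initiation or CT scan (whichever is earlier) and all post-biologic therapy information will be included".

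For the final analysis, Section 5.2 sets a condition on one side of the comparison: "patients who do not have accessible adequate follow-up information (4 or more months from drug initiation with clear documentation of response) will be excluded". Section 5.1 asks for age, an asthma diagnosis, a biologic taken and a chest CT. It asks for no prior time in the health system.

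The synopsis describes Michigan as a tertiary academic centre, and says that the Calgary site "is tertiary academic medical referral center for patients with severe asthma". Its primary endpoint separates patients with any reduction in exacerbation frequency from those without. Table 1 lists only an unchanged value as non-response and does not place an increase.

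**The concern.** The label is a within-patient comparison, so both windows have to be observed. The plan enforces this only after initiation.

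The fallback is triggered by exactly one encounter in the year. Two visits in the last six weeks do not trigger it, and that patient is scored as though a year had been seen. A patient with a single encounter in the whole record, or none before the biologic, is not covered either. The time frame is noted only in fallback cases, and Section 6 never uses it. No section gives the denominator for exacerbation frequency or says how events treated elsewhere are captured.

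Events missing from the baseline make a real reduction harder to show. Section 4.1 aims to isolate the roughly 15% who do not respond, about 45 of 300 at Michigan (0.15 × 300). In a class that small, misplaced improvers matter. The models in Section 6.3 would be trained partly on how long a patient had been under the centre's care. That may also differ between the cohorts, since Section 4.2 calls Calgary's prospectively constructed.

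**Working it through.** The plan gives no exacerbation rate, treatment effect or share of recent referrals, so there is no figure of its own to reproduce. The calculation below is illustrative.

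**Inputs from the plan.** Baseline window 12 months. Response window 18 − 4 = 14 months. Responder = any decrease.

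**Assumptions not in the documents.** True rate 3 per year; rate ratio RR on treatment 0.5 or 1; Poisson counts; m baseline months observed, with no events recorded for the rest; response window fully observed.

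**Model.** Baseline count Y0 ~ Poisson(3 × m/12), with mean 3, 2 or 1 for m = 12, 8 or 4. Response count Y1 ~ Poisson(3 × RR × 14/12), with mean 1.75 (RR 0.5) or 3.5 (RR 1).

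**Two readings of the average.** Nominal year: responder if Y1/14 < Y0/12. Observed months: responder if Y1/14 < Y0/m.

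Exact probability of being labelled a responder:

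| Observed baseline months | RR 0.5, nominal | RR 0.5, observed | RR 1, nominal | RR 1, observed |
|---|---|---|---|---|
| 12 | 79% | 79% | 50% | 50% |
| 8 | 63% | 69% | 33% | 47% |
| 4 | 39% | 59% | 16% | 45% |

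**Why an effect remains with observed months.** A zero baseline cannot decrease. The chance of an empty window is exp(−3) = 5% for 12 months, exp(−2) = 14% for 8 and exp(−1) = 37% for 4.

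**How the label is reached.** At 4 months, RR 0.5 and a nominal year, 61% show no reduction: about 6 points are ties and 55 are apparent increases. Those increases are non-response under the synopsis endpoint, but have no category in Table 1.

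**Losses in the other window.** With a full baseline but only two-thirds or one-third of response-window events captured, the labelled responders rise to 87% and 93% (RR 0.5), or 69% and 87% (RR 1). With two-thirds captured in both windows and nominal window lengths as divisors, they are 74% against 79% (RR 0.5) and 52% against 50% (RR 1).

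**Scale in a cohort of 300.** Assume 85% have RR 0.5 and 15% have RR 1.
- Full baselines: 0.85 × 21.4% + 0.15 × 49.9% = 25.7%, or 77 patients, show no decrease.
- With only 3 observed months the proportion is 72.4% (nominal) or 49.7% (observed).
- If 10% to 40% of patients are in that position, the count rises from 77 to between 91 and 133 (nominal) or between 84 and 106 (observed).

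**The case against.** **Events elsewhere may not be lost.** All available EMR information is abstracted. Section 4.1 counts a temporary OCS or ICS increase of three or more days as an exacerbation without requiring a visit at the centre, and Section 7.1.8 has two physicians adjudicate. History notes may fill part of the gap. This stands, and treating the missing months as empty is the unfavourable case. But no rule requires such events to be abstracted, or to be handled alike in both windows.

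**The denominator is not stated.** Section 4.1 does not say to divide by a nominal 12 months. Dividing by observed months shrinks the effect considerably, and nearly removes it when the rate does not change. This also stands, so both readings are shown.

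**The direction is not fixed.** Lost response-window events push towards responder. So does referral prompted by an exacerbation, or a fallback baseline built from two exacerbation visits. Roughly equal loss in both windows largely cancels.

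**Stronger readings the documents do not support.** A reader might infer that recent referrals are in fact undercounted and labelled non-responders. Nothing in the plan gives their number, where they were treated before, or what their charts record. A reader might also take both sites to be referral centres, but only Calgary is so described. Nor does the plan give any reason why time under care should relate to chest-wall measures, so mislabelling is shown to be possible but bias in the biomarker association is not.

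**Conclusion.** The asymmetry is plain in the text: follow-up is a condition of the final analysis and an observed baseline is not, and the fallback does not close the gap. Followed as written, the plan can class true improvers as having no reduction. This goes beyond missing detail, because it affects the primary label.

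Under the assumptions above, cutting the observed baseline from 12 to 4 months lowers correct labelling of improvers by 40 percentage points on a nominal-year reading (79% to 39%) and by about 19 on an observed-months reading (78.6% to 59.5%). The effect is therefore real under either reading, but its size depends on the unstated denominator. The net direction in the actual cohort and the share of patients affected are unknown. It should be corrected as a risk of unknown size.

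**What to change.** - Record the date of the first encounter in the health system. Start baseline observation at the later of that date and 12 months before initiation.
- Define exacerbation and hospitalization frequency as events per observed month in both windows.
- Count outside events documented in notes by the same rule in both windows and both cohorts.
- Exclude from these two endpoints patients with no observed or documented baseline.
- Add a sensitivity analysis restricted to patients whose 12-month baseline is fully observed or documented. Observed months alone do not solve the empty-window problem, so this analysis is needed as a check.

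The cost is one extra date per patient, a little more analysis, and a few patients leaving the two event-count endpoints. Making a full 12 months compulsory in the main analysis is a debatable trade: it would drop an unknown share of about 300 patients and could introduce selection. The restriction therefore fits better as a sensitivity analysis.

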Secondary Objectives:	
1. To identify imaging biomarkers that are associated with the probability of any post-treatment improvement of FEV1 of 5% or more2. To identify imaging biomarkers that are associated with the probability of any post-treatment reduction in maintenance OCS use							
Exploratory Objectives:	
1. To identify imaging biomarkers that are associated with the probability of any reduction in pre-treatment baseline hospitalizations for asthma2. To identify imaging biomarkers that are associated with the probability of any post-treatment improvement in ACT score3. To identify imaging biomarkers that are associated with the probability of any subjective post-treatment reduction in symptoms described clinically							
Endpoints:	Primary Endpoint:	Determine the cutoff value in chest wall muscle size/quality that optimally classifies patients that had and did not have any reduction in pre-treatment baseline exacerbation frequency (binary). Alternative (continuous): determine the strength of the linear/non-linear relationship						

	between continuous chest wall muscle size/quality and continuous change in exacerbation frequency
Secondary Endpoints:	
 1. Determine individual and combinations of body composition measures (phenotypes) associated with a 5% or greater improvement in FEV1 when compared to baseline FEV1 2. Determine individual and combinations of body composition measures associated with any reduction in maintenance OCS use when compared to baseline OCS use
Exploratory Endpoints:	
These endpoints may be limited in scope of analysis by the sample size within each of the outcome groups.
 
 1. Determine individual and combinations of body composition measures associated with any reduction in hospitalizations when compared to baseline hospitalizations 2. Determine individual and combinations of body composition measures associated with any improvement in ACT score when compared to baseline ACT score 3. Determine individual and combinations of body composition measures associated with any subjective improvement of symptoms when compared to baseline symptoms

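### The primary responder label compares a 12-month baseline with a 14-month response window that a switch or add-on can shorten, and no readable text gives the exacerbation measure a time denominator

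*Combined protocol and SAP*

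**What the plan says.** Section 4.1 sets the two periods. For baseline, "we will define baseline measurements as the average of all data obtained in the year prior to biologic initiation". For response, "we will use the average of all data from 4 to 18 months after biologic initiation". If only one encounter is available at baseline, "the average of the 2 clinical encounters immediately prior to biologic initiation will be used with the time frame noted in the database". The matching fallback for response is "the average of the 2 clinical encounters closest to, but not before 4 months after, biologic initiation", with no note of its time span. When a second biologic is added or the first is changed, "we will use all clinical data prior to the change, even if it is before 4 months of use".

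Table 1 in Section 4.1 makes any fall in exacerbations or hospitalizations a response. The Section 1.1 synopsis asks for the cutoff that "optimally classifies patients that had and did not have any reduction in pre-treatment baseline exacerbation frequency (binary", with a continuous change in frequency as the alternative. The Section 3 endpoint column speaks only of fewer exacerbations. Section 6 has no rate, person-time or offset term.

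Section 5.2 drops patients with less than 4 months of documented follow-up from drug initiation from the final analysis, but keeps them for cluster identification.

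**The concern.** Exacerbations are discrete events, so their total grows with time observed. An average of events needs a divisor, and it could be months, years or encounters. Two analysts could follow this text and give the same patient opposite primary labels.

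The threshold makes this sharper, because any fall counts and a single event can decide the label. Window length is also unlikely to be unrelated to outcome. Section 2.1 describes partial and non-responders as the patients who are switched, and Section 4.1 codes ineffectiveness as a reason for stopping. Section 4.1 also says that "our interest is primarily in finding the ~15% of patients who do not respond to biologics", so errors in that small class bear directly on the study's aim. The continuous alternative has the same weakness if it is built on counts.

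**Working it through.** The plan gives no event rate, switch rate or power figure for this endpoint, so it offers no figure to reproduce.

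**From Section 4.1.** Baseline is 12 months. The full response window is 18 − 4 = 14 months. Any fall is a response. An increase is treated here as non-response, which follows the synopsis.

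**Assumed.** Baseline count B ~ Poisson(r) and response count R ~ Poisson(r × ρ × T/12), independent, where T is the response window in months. The rate r is 2 a year (1 to 4 tried). ρ = 1 is no true change and ρ = 0.5 a true halving.

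**Formulas.**
- Counts: P(R < B).
- Annualised rates: P(R/T < B/12).
- Event-driven switching, represented by at least one event in the window: P(1 ≤ R < B) / P(R ≥ 1) on counts, and likewise on rates.

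**Step 1: expected counts.** With no true change, the expected count differs from baseline by (T − 12)/12. That is +17% at 14 months, −50% at 6 and −67% at 4, at any event rate, provided window length is independent of events.

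**Step 2: full window, no switching, no true change.**

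| Scored responder | 1/year | 2/year | 4/year |
|---|---|---|---|
| Counts, 14 v 12 months | 31% | 34% | 34% |
| Annualised rates, 14 v 12 months | 49% | 52% | 48% |
| Equal 12-month windows | 35% | 40% | 43% |

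At 2/year the gap between the first two rows comes from ties. The probability of equal non-zero counts is 0.183, and annualising turns each such tie into a fall: 0.340 + 0.183 = 0.523. With patient-level gamma overdispersion of 0.8 at 2/year, the three rows become 30%, 44% and 35%.

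**Step 3: shortened window, no true change, 2/year (1/year to 4/year in brackets).**

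| Scale and switching | 4 months | 6 months |
|---|---|---|
| Counts, independent of events | 69% (52–83) | 61% (47–73) |
| Counts, at least one event | 50% (23–78) | 45% (22–69) |
| Rates, independent of events | 49% (46–49) | 45% (41–46) |
| Rates, at least one event | 10% (2–31) | 20% (6–38) |

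Check of the second row at 4 months: P(R = 0) = exp(−2/3) = 0.513 and P(B ≥ 1) = 0.865. So P(1 ≤ R < B) = 0.688 − 0.513 × 0.865 = 0.244, and 0.244/0.487 = 0.50.

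A window of 4 or 6 months arises from a change at month 4 or 6 if data from initiation are used, or at month 8 or 10 if the month-4 start is kept. Both meet a 4-month follow-up requirement. At 1 and 2 months, rates with independent switching give 73% and 62%. Those figures matter only if such patients are analysed.

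**Step 4: comparison with a real benefit.** A true halving over 14 months has expected count 2 × 0.5 × 14/12 = 1.17, the same as no change over 7 months. On counts it is scored a response 57% of the time at 2/year (45% at 1/year, 68% at 4/year).
- Independent switching: unchanged patients at 4/6 months score higher at every rate tried (52/47% v 45%, 69/61% v 57%, 83/73% v 68%).
- Event-driven switching: the order reverses at 1/year (23/22% v 45%) and 2/year (50/45% v 57%), and holds at 4/year (78/69% v 68%).

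**The case against.** The strongest reply is that the plan already means a rate. The synopsis says frequency, Section 4.1 averages both periods, and an average is not a sum. Figure 4, which sets out the baseline and response data plan, is not shown and may settle the matter. This has weight, and a demonstrated count bias cannot be claimed. But the rate reading does not remove the problem: with 14 months against 12 it moves unchanged full-window patients from 34% to 52%. A per-encounter average, which the two-encounter fallback could suggest, is a third reading, not modelled here.

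Second, Section 5.2 may supply the minimum window. It may, but it conflicts with the explicit use of pre-month-4 data in Section 4.1. It also leaves the 4- and 6-month results standing.

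Third, the threshold itself causes much of the mislabelling, since 40% of unchanged patients score as responders even with equal windows. That is true and remains after the fix. The avoidable part is the dependence on window length and scale.

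Fourth, Section 2.1 describes general practice and says partial responders are switched too. Section 4.1 counts those as responders, so short windows are not confined to the non-responder class.

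A reader might infer that unchanged patients who switch are generally scored better than full-window patients who truly improved. The documents do not support that. In this illustration it holds only on counts, and then only if switching is independent of events or event rates are high.

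**Conclusion.** The concern holds as a defect in a stated rule: unequal windows, a shortened window after a switch or add-on, and no readable time denominator for the primary label. At an assumed 2 events a year with no true change, the choice between counts and rates moves the full-window responder proportion by 18 points (34% to 52%). Short windows shift it up on counts if switching is independent of events, and sharply down on rates if a switch follows an event. Direction and size therefore depend on the scale and on why patients switch, neither of which the plan fixes.

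The percentages rest on assumed Poisson counts and rates of 1 to 4 a year; overdispersion lowers them but leaves the full-window ordering unchanged. A reader might want a number of mislabelled patients. None can be derived, because the documents give no switch frequency or event rate.

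Sections 4.1 and 5.2 disagree on whether patients who change biologic before month 4 enter the final analysis, and must be reconciled. The point should be fixed before labels are derived. Confidence is medium, because the intended scale may be a rate and Figure 4 cannot be read.

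**What to change.** 1. Define exacerbations and hospitalizations as events per observed person-time in both periods. Use the actual calendar span when the two-encounter fallback applies, and record that span for the response period as well.
2. Because annualising 14 against 12 months turns equal non-zero counts into falls, use equal 12-month windows for patients who have them, either as the primary comparison or as a pre-specified key sensitivity analysis.
3. State one minimum observed window for the primary analysis that reconciles Sections 4.1 and 5.2, and say whether a shortened window starts at initiation or at month 4.
4. Report shorter courses separately, by the end reason already coded.

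The cost is SAP wording and one person-time variable derived from the abstracted records. The primary set may be slightly smaller, by an amount the documents do not allow one to state. Two months of response data go unused in the equal-window comparison. Person-time alone does not make the label independent of window length: rates from short windows stay noisy, and they under-score patients whose switch follows an event, which is why items 2 to 4 belong with item 1.
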